5.5 Replacement of Participants

Participants who do not meet eligibility criteria at Baseline will not receive any study drug and will be considered screen failures. Participants who withdraw from the study for any reason will not be replaced.

6 TREATMENT OF PARTICIPANTS

6.1 Treatment Arms

In this single-blind, 4-period study, 15 participants will be enrolled and will be treated with the following during the 4 periods of the study.

- Ergoloid mesylates 1 mg TID (Medisca)* and matching placebo for 5-Hydroxytryptophan 100mg TID***
- Ergoloid mesylates 1 mg TID (Medisca) and 5-Hydroxytryptophan 100 mg TID (5-HTP, Basic Vitamins)**
- 5-Hydroxytryptophan 100 mg TID (5-HTP, Basic Vitamins) and matching placebo for Ergoloid mesylates 1mg TID***
- Matching placebo for Ergoloid mesylates 1mg TID and Matching placebo for 5-Hydroxytryptophan 100mg TID ***

* 1 mg will be mixed with methyl cellulose and placed in a size 00 capsule ** will be over-encapsulated in identical size 00 capsules ***will be ascorbic acid powder in identical size 00 capsules

All study medications will be prepared at the RUMC research pharmacy and provided as identicalappearing capsules in bottles. Two bottles of capsules will be provided at each visit and one capsule from each bottle will be taken 3 times a day. Doses should be taken at least 4 hours apart.

6.2 Study Medications

The Ergoloid Mesylate is provided as powder manufactured by Medisca and 5-HTP 100 mg capsules available to the RUMC pharmacy are manufactured by Basic Vitamins. All study medications and their matching placebos will be compounded and over-encapsulated at the Rush Oak Park Compounding Pharmacy.

6.3 Drug Accountability

The Investigator or designated study personnel will be responsible for keeping accurate records of the study drugs (and other components) used in this study. These records will include documentation of receipt, inventory, and disposition to participant. The records should include dates, quantities, batch/serial numbers, expiration dates (if applicable), and any unique code numbers assigned (if applicable).

All drug returned will be disposed of by the study team after medication reconciliation to determine compliance. Amount of drug returned and disposed will be recorded in the participant study binders. In accordance with Good Pharmacy Practices, gloves will always be worn by study personnel when handling study drug.

6.4 Blinding

This is a single-blind study, meaning the participant and his family/caregivers will not know what drug or combination the participant is receiving. The investigator and study coordinator will know what drug the participant is taking. The remainder of the study team performing assessments such as the Vineland, eye tracking, ERP, Toolbox, and the KiTAP will not know the type of treatment the patient is on when testing is done.

The PI or designee will be responsible for maintaining the single blind, consistent with protocol design, throughout the study, except in the case of an emergency need to unblind the participant for medical reasons. Blinding is not to be broken during the study unless considered necessary by the Investigator for emergency situations for reasons of participant safety. When the blind is broken, the reason must be fully documented.

6.5 Study Drug Administration

Two capsules will be taken orally in the morning, afternoon and evening. Doses should be taken at least 4 hours apart.

6.6 **Prior and Concomitant Medications**

A prior medication is defined as any psychotropic or anti-epileptic medication taken by the participant for more than 28 days during the 6 months prior to first dose of study drug (Day 1), which was subsequently discontinued within that same 6 month period.

A concomitant medication is defined as any medication taken 14 days prior to the first dose of study drug (Day 1) and during the study through the Week 14 Follow-up Visit. Concomitant medications should be recorded with indication, daily dose, and start and stop dates of administration.

Current treatment with no more than 3 prescribed psychotropic medications is allowed. Antiepileptic medications are permitted and are not counted as psychotropic medications if they are used for treatment of seizures. Anti-epileptics for other indications, such as the treatment of mood disorders, count towards the limit of three permitted medications. Permitted concomitant psychotropic medications must be at a stable dose and dosing regimen for at least 2 weeks prior to the commencement of study medication.

Anti-epileptic medications must be at a stable dose and dosing regimen for 12 weeks prior to Screening and must remain stable during the period between Screening and the commencement of study medication.

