This is a single-center, Phase 2, single-blind, 4-period sequential study will obtain a preliminary assessment of the effects of ergoloid mesylates (EM) 1 mg TID and 5-hydroxytryptophan (5-HTP) 100 mg TID and the combination compared to a placebo period in participants with Fragile X Syndrome. The study will consist of a Screening period of up to 28 days prior to initial study drug administration, followed by four 4 week single-blind treatment periods. The screening and baseline visits may occur at the same time, provided the results of safety labs can be obtained. A final follow-up visit or phone contact for safety is planned one week after the conclusion of Period 4.

Eligible participants will be started on EM for 4 weeks in Period 1, then will take EM and 5-HTP for 4 weeks in Period 2, then, 5-HTP for 4 weeks in Period 3, then placebo for 4 weeks in Period 4. Study visits will occur at baseline and every 4 weeks at transition times between periods, then at the end of the study.

Brief cognitive and behavioral assessments will be performed during each clinic visit. Safety and tolerability assessments will include adverse event monitoring, vital signs, blood chemistry and hematology, and urinalysis.

	4 Weeks Period 1	4 Weeks Period 2	4 Weeks Period 3	4 Weeks Period 4		
Screen/Enroll ───→	EM	EM + 5-HTP	5-HTP	Placebo		
N=15 participants						
EM=ergoloid mesylates 1 mg TID, 5-HTP = 5-hydroxytryptophan 100 mg TID						
Planned Numbers of Participants						
Enrollment of a total of 15 eligible participants is planned.						
Study Duration						
The total duration of the study for each participant will be up to 21 weeks, including a maximum of 4-week screening						

The total duration of the study for each participant will be up to 21 weeks, including a maximum of 4-week screening period, four 4-week Single-Blind treatment Periods, and a follow-up telephone call approximately 1 week after the last treatment visit.

Study Procedures:

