4 INVESTIGATIONAL PLAN

4.1 Overall Study Design

This is a single center, Phase 2, single-blind, 4 period study to obtain preliminary assessment of the effects of ergoloid mesylates (EM), 5-hydroxytryptophan (5-HTP), and the combination in participants with Fragile X Syndrome. As schematic display of the study design is shown in Figure 7.

The study will consist of a Screening period of up to 28 days prior to initial study drug administration, followed by four 4-week single-blind treatment periods. The screening and baseline visits may occur at the same time, provided the results of safety labs can be obtained. No washout period will be utilized between treatment periods. A final follow-up phone contact for safety is planned one week after the conclusion of Period 4.

Eligible participants will be started on over-encapsulated EM 1 mg TID during Period 1, then will take EM 1 mg TID and 5-HTP 100 mg TID in Period 2, then 5-HTP 100 mg TID in Period 3, and placebo in Period 4. Throughout all 4 periods, participants will take two identical capsules three times a day. If only taking one over-encapsulated drug, they will take one over-encapsulated placebo pill with the drug at each dose, and when in period 4 they will take two over-encapsulated placebo pills at each dose.

Cognitive and behavioral assessments will be performed during each clinic visit. Safety and tolerability assessments throughout the study will include adverse event monitoring, vital signs, blood chemistry, hematology, and urinalysis.

Figure 7 Study Design Schematic

N=15 participants

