5.2 Participant Inclusion Criteria

- 1. Participant is male aged 18 to 45 years, inclusive.
- 2. Participant has Fragile X Syndrome with a molecular genetic confirmation of the full Fragile X Mental Retardation 1 (FMR1) mutation (≥200 CGG repeats).
- 3. Current treatment with no more than 3 prescribed psychotropic medications. Anti-epileptic medications are permitted and are not counted as psychotropic medications if they are used for treatment of seizures. Anti-epileptics for other indications, such as the treatment of mood disorders, count towards the limit of permitted medications.
- 4. Permitted concomitant psychotropic medications must be at a stable dose and dosing regimen for at least 2 weeks prior to Screening and must remain stable during the period between Screening and the commencement of study medication.
- 5. Anti-epileptic medications must be at a stable dose and dosing regimen for 12 weeks prior to Screening and must remain stable during the period between Screening and the commencement of study medication.
- 6. Participants with a history of seizure disorder who are currently receiving treatment with anti-epileptics must have been seizure-free for 3 months preceding screening or must be seizure-free for 3 years if not currently receiving anti-epileptics.
- 7. Behavioral and therapy treatments/interventions must be stable for 4 weeks prior to Screening and must remain stable during the period between Screening and the commencement of study medication, and throughout the study. Minor changes in hours or times of therapy that are not considered clinically significant will not be exclusionary.

Changes in therapies provided through a school program, due to school vacations, are allowed.

- 8. Participant must be willing to practice barrier methods of contraception while on study, if sexually active. Abstinence is also considered a reasonable form of birth control in this study population.
- 9. Participant has a parent, legal authorized guardian or consistent caregiver.
- 10. Participant and caregiver are able to attend the clinic regularly and reliably.
- 11. Participant is able to swallow tablets and capsules.
- 12. For participants who are not their own legal guardian, participant's parent/legal authorized guardian is able to understand and sign an informed consent form to participate in the study.
- 13. If participant is his/her own legal guardian, he/she can understand and sign informed consent to participate in the study.

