6.7 Other Therapeutic Treatments

Behavioral and therapy treatments/interventions must be stable for 4 weeks prior to Screening and must remain stable during the period between Screening and the commencement of study medication, and throughout the study.

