9.3.4 Week 17 (Period 4, Final Contact at End of Study)

- Telephone call to:
 - Record any updates to concomitant medication use,
 - Assess and record any adverse events, and
 - Record final participant disposition.

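### Background psychotropic and anti-epileptic doses need be stable only until the first study dose, so changes during the 16 treatment weeks break no stated rule; any that occur and persist would be most common at the placebo visit, which is always last

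*Combined protocol and SAP*

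**What the plan says.** **Drugs.** Inclusion item 4 (synopsis and section 5.2) requires psychotropics to be stable for "at least 2 weeks prior to Screening and must remain stable during the period between Screening and the commencement of study medication". Item 5 has the same end point for anti-epileptics, with a 12-week window before Screening. Section 6.6 repeats the anti-epileptic rule, but for psychotropics it asks only for a "stable dose and dosing regimen for at least 2 weeks prior to the commencement of study medication". Its two weeks therefore count back from first dose, where item 4 counts them back from Screening.

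**Behavioral therapies.** Section 6.7 says these "must remain stable during the period between Screening and the commencement of study medication, and throughout the study". Inclusion item 7 agrees and adds a tolerance: "Minor changes in hours or times of therapy that are not considered clinically significant will not be exclusionary". Changes caused by school vacations are also allowed.

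**Other rules during treatment.** Exclusion item 4 (section 5.3) bans CYP3A4 inhibitors, beta-blockers, MAO inhibitors and triptans. The medication-related reason for mandatory withdrawal in section 5.4 is the need for a prohibited drug. Section 10.4 plans descriptive summaries by time point and does not mention medication changes. The completers set in section 10.3 excludes significant protocol violations without defining them.

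**Design.** All participants take EM, EM + 5-HTP and 5-HTP, "then placebo for 4 weeks in Period 4" (synopsis, Study Design). Section 4.1 adds: "No washout period will be utilized between treatment periods". All visits are compared with one Day 1 baseline.

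**Recording.** Section 6.6 defines concomitant medication as running "during the study through the Week 14 Follow-up Visit". The schedule in section 14.1 has no such visit and collects medications to Week 17, where section 9.3.4 says: "Record any updates to concomitant medication use".

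**The concern.** The protocol controls one kind of co-intervention during treatment (behavioral therapy) and not the other (background drugs), and gives no reason for the difference. Section 3.1 names stimulants, SSRIs and atypical antipsychotics as usual care for attention problems, anxiety and aggression. KiTAP, ADAMS and ABC measure those areas, so a dose change could move the outcomes directly.

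In a design with randomized period order, such changes would fall on all treatments alike on average. Here the order is fixed. A lasting change made in any period after the first is present at the placebo visit but absent from at least one active visit, and so enters at least one placebo contrast. The direction cannot be predicted. A drug increased after worsening could improve the placebo visit and hide a benefit; a drug stopped during an earlier good period could worsen it and exaggerate one.

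**Working it through.** **1. Is there a rule after first dose?** Setting the provisions side by side:

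| Provision | Covers | Ends at |
|---|---|---|
| Inclusion 4 | Psychotropics | First study dose |
| Inclusion 5 | Anti-epileptics | First study dose |
| Section 6.6 | Both | First study dose |
| Inclusion 7, section 6.7 | Behavioral therapies | End of study |
| Exclusion 4 | Four named drug classes | End of participation |

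No row covers re-dosing or stopping a permitted psychotropic or anti-epileptic after first dose. Section 6.6 is ambiguous on starting a new one: its pre-dose stability wording could be read as a bar, but no sentence says so.

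**2. Which changes affect a placebo contrast?** The plan gives no figure to reproduce, so what follows is an illustration.

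Inputs from the documents: N = 15; four 4-week periods; placebo fourth.

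Assumed inputs: chance p of a change per period = 2%, 5% or 10%; effect d of a change = 0.25, 0.5 or 1 SD; every change lasts, has a constant effect, and acts in the same direction.

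Share changed by the end of period k: c_k = 1 − (1 − p)^k.

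| p | c_1 (EM) | c_2 (EM + 5-HTP) | c_3 (5-HTP) | c_4 (placebo) |
|---|---|---|---|---|
| 2% | 0.020 | 0.040 | 0.059 | 0.078 |
| 5% | 0.050 | 0.098 | 0.143 | 0.185 |
| 10% | 0.100 | 0.190 | 0.271 | 0.344 |

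Multiplied by 15, this is 0.3 to 1.5 participants changed by the EM visit and 1.2 to 5.2 by the placebo visit.

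Shift in the placebo contrast against period k: d × (c_4 − c_k). The subtraction matters: a lasting Period 1 change with a constant effect is present at all four visits and cancels.

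| Contrast | Lowest (p = 2%, d = 0.25) | Middle (p = 5%, d = 0.5) | Highest (p = 10%, d = 1) |
|---|---|---|---|
| Placebo − EM | 0.25 × 0.058 = 0.014 | 0.5 × 0.135 = 0.07 | 1 × 0.244 = 0.24 |
| Placebo − (EM + 5-HTP) | 0.25 × 0.038 = 0.01 | 0.5 × 0.088 = 0.04 | 1 × 0.154 = 0.15 |
| Placebo − 5-HTP | 0.25 × 0.019 = 0.005 | 0.5 × 0.043 = 0.02 | 1 × 0.073 = 0.07 |

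All shifts are in SD units. Put another way, each participant who changes between Weeks 4 and 16 moves the placebo-minus-EM mean by d/15, or 0.067 SD when d = 1 SD.

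**3. Compared with the noise.** Paired standard error = √(2(1 − r)/15), with r an assumed within-person correlation. For r = 0.5, 0.7 and 0.8 this is 0.26, 0.20 and 0.16 SD. The middle placebo-minus-EM shift is 0.068/0.20 ≈ 0.34 of a standard error, and the other two contrasts are smaller.

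**The case against.** The case for leaving the text alone is substantial.

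- The study is exploratory and descriptive, with no hypothesis test and no sample-size target (sections 10.1 and 10.4). Fixed order confounds time with treatment whatever is done about background drugs. **This stands**, and it limits the point to a minor one.
- Section 3.4.1 frames the objectives for participants on their usual medicines, so the freedom to adjust may be deliberate. **Possible**, but the text does not say so.
- Drug, indication, dose and dates are already recorded, with updates at every call and visit, so changes could be listed afterwards. **This stands**, except that the reason for a change is not among the listed items and the handling would be chosen after the data are seen.
- A rule with a clinical-need exception would still allow a drug to be increased after worsening. **This stands**: the clause restrains mainly elective changes.

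The documents also do not support several stronger readings that a reader might infer:

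- *That changes will accumulate at placebo.* This holds only if changes occur and persist. Reversed changes do not add up.
- *That placebo carries four times the bias of the EM visit, because 16 weeks have passed and not 4.* Those are elapsed weeks, not a measure of bias.
- *That the unblinded investigator steers background prescribing.* Section 6.4 says the investigator knows the treatment, but the documents do not say who prescribes background drugs.
- *That medication data stop at Week 14, before the placebo visit.* Sections 9.3.3, 9.3.4 and 14.1 collect them to Week 17. The Week 14 wording is a clerical slip.

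**Conclusion.** The gap in the text is real: stability of background psychotropics and anti-epileptics is required only up to first dose, and no prohibition, withdrawal or analysis rule covers a later re-dosing or stop. Whether a change would count as a significant violation for the completers set is undefined, so that robustness check may not pick it up.

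The consequence is conditional, and its size and direction cannot be obtained from the documents. Across the assumed inputs the shift runs from about 0.01 to 0.24 SD against EM, 0.01 to 0.15 SD against EM + 5-HTP and 0.005 to 0.07 SD against 5-HTP. The upper ends need a 10% change rate per period, a full 1 SD effect each time, and every change lasting and in one direction; mixed directions would partly cancel.

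This is a cheap improvement and not a serious flaw. It would reduce one avoidable part of the time confounding. It would not by itself make the placebo contrast interpretable.

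**What to change.** 1. In inclusion items 4 and 5 (synopsis and section 5.2) and in section 6.6, add that background psychotropic and anti-epileptic drugs and doses stay unchanged, and no new ones start, through the Week 16 visit unless clinically needed. State that a needed change does not force withdrawal.
2. Align the psychotropic window in section 6.6 with item 4: two weeks before Screening, then stable to first dose.
3. Record the reason for any change.
4. In section 10.4, list changes by period. As a sensitivity summary only, show each measure with and without visits after a change. Leave the completers definition at participant level.
5. As a clerical correction, replace the Week 14 visit in section 6.6 with the Week 17 final contact.

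**Cost.** A few sentences in an amendment and one added data field. Some non-urgent medication changes would wait up to 16 weeks. The sensitivity summary loses mostly late visits (in the illustration, 1.2 to 5.2 of 15 at placebo against 0.3 to 1.5 at EM). If changes follow worsening, that loss is informative, so the summary should be read beside the full one and not replace it.

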6.7 Other Therapeutic Treatments

Behavioral and therapy treatments/interventions must be stable for 4 weeks prior to Screening and must remain stable during the period between Screening and the commencement of study medication, and throughout the study.

6.8 Dietary Guidelines

There are no dietary restrictions. Participants should follow their usual eating behaviors.

6.9 Lifestyle Guidelines

There no lifestyle restrictions or guidelines associated with this study.

7 STUDY PROCEDURES AND ASSESSMENTS

The study will be conducted in accordance with the CFRs (21 CFR § 11, 50, 54, 56, and 312 Subpart D), which originate from the ethical principles laid down in the current revision of the Declaration of Helsinki, Good Clinical Practice (GCP),^{26,27} and the policies and procedures as outlined by the ethical requirements for IRB review and informed consent form.

7.1 Informed Consent

Informed consent will be obtained prior to the participant entering into the study and before any protocol-directed procedures are performed.

7.2 Medical /Surgical History

Medical/Surgical history will be recorded at the Screening Visit as specified in Section 10.2. Participant eligibility will be evaluated to determine all inclusion and none of the exclusion criteria are met. The Investigator will inquire with the participant on Period 1/Day 1 (Baseline, prior to

randomization) to determine if there have been any changes in the participants' s health affecting eligibility or requiring an update to their medical and surgical history.

7.3 Demographics and Social History

Demographics (sex, ethnicity, race) and social history (tobacco, alcohol, and/or drug use) will be recorded at the Screening Visit as specified in the Schedule of Assessments.

7.4 Stanford Binet Intelligence Scale

The Stanford Binet Intelligence Scale – Version 5 will be administered at Screening in order to support characterization of the study cohort and to determine whether cognitive and behavioral responses are dependent on baseline level of cognitive functioning. The scale will be scored according to the Hessl z-deviation method to prevent floor effects.²⁸

7.5 Physical Examination (Full and Abbreviated)

The full physical examination will be conducted at the Screening as specified in the Schedule of Assessments and will include:

- General appearance
- Skin
- Eyes, ears, nose, and throat (EENT)
- Head/neck
- Extremities
- Musculoskeletal examination
- Respiratory examination
- Cardiovascular assessment including rhythm and presence of cardiac abnormalities
- Abdominal examination
- Basic neurologic examination
- Any additional assessments necessary to establish baseline status or evaluate symptoms or adverse experiences

An abbreviated physical examination will be conducted at Period 1/Day 1 (if not the same day as Screening) and at the visit at the end of each Period and will include:

- Any changes noted since the initial physical examination
- General appearance
- Skin
- Extremities
- Respiratory examination
- Cardiovascular assessment including rhythm and presence of cardiac abnormalities
- Abdominal examination

Significant findings prior to the start of dosing will be recorded on the Medical History page of the CRF. Only changes from baseline physical examination findings that meet the definition of a treatment-emergent AE will be recorded as an AE.

